SAP	Statistical Analysis Plan
SAS	Statistical Analysis Software
SpO2	Peripheral capillary oxygen saturation
TEAE	Treatment-emergent adverse event
TESAE	Treatment-emergent serious adverse event
TID	Three times daily
TNF α	Tumor necrosis factor alpha
WHO	World Health Organization

1 INTRODUCTION

The purpose of this Statistical Analysis Plan (SAP) is to provide a description of the statistical methods to be implemented for the analysis of data from the study with protocol number AKB-9778-CI-6001. The SAP will be finalized prior to database lock. Any deviations from the SAP after database lock will be documented in the final Clinical Study Report (CSR).

2 STUDY OVERVIEW

2.1 Study Objectives

2.1.1 *Primary Objective*

The primary objectives of this study are to assess the safety and efficacy of razuprotafib in subjects with moderate to severe COVID-19.

2.1.2 *Secondary Objectives*

The secondary objectives of this study are to examine the effects of razuprotafib on biomarkers of inflammation and coagulopathy (ie, C-reactive protein [CRP] and D-dimer) in the plasma of subjects with moderate to severe COVID-19 and to characterize exposure of razuprotafib based on plasma concentrations for the samples collected on Day 1 and Day 6.

[figure not shown]
2.1.3 *Exploratory Objectives*

The exploratory objective of this study is to examine the effects of razuprotafib on biomarkers of vascular leakage and inflammation (ie, Angpt-2, IL-6, IL-8, tumor necrosis factor alpha [TNF α], and high mobility group box 1 [HMGB-1]) in the plasma of subjects with moderate to severe COVID-19.

2.2 Study Design

2.2.1 *Overview*

This is a Phase 2, randomized, double-blind, placebo-controlled, parallel-group, multicenter, dose escalation and proof-of-concept study to evaluate the safety and efficacy of razuprotafib, administered three times daily (TID) (every 8 hours [Q8H]), in hospitalized subjects with moderate to severe COVID-19 receiving standard of care therapy. The study design is summarized in the figure below.

2.2.2 Randomization and Blinding

After eligibility is determined, 30 subjects (6 sentinel subjects) will be randomized in a 1:1:1 ratio to 1 of the treatment groups in Part 1, Step 1:

- Razuprotafib 10 mg TID;
- Razuprotafib 20 mg TID; or
- Placebo TID.

If the Data Review Committee (DRC) recommends that Part 1, Step 2 should proceed as planned, then another 30 subjects (6 sentinel subjects) will be randomized in a 1:1:1 ratio (or a 2:1 ratio if only 1 razuprotafib dose level is chosen) to 1 of the treatment groups in Part 1, Step 2:

- Razuprotafib 20 mg TID;
- Razuprotafib 30 mg TID; or
- Placebo TID (the placebo volume will match the active volume for each treatment group).

Note: The planned dosing for Part 1, Step 2 may be changed after the DRC reviews the safety and PK data from Part 1, Step 1.

Based on the DRC's review of the available safety and PK data from Part 1, Step 1 and Part 1, Step 2, the study will proceed to Part 2. In Part 2, 120 subjects will be randomized to 1 of the treatment groups (dose 1 razuprotafib TID, dose 2 razuprotafib TID [optional], or placebo TID) in a 1:1:1 ratio (or a 2:1 ratio [razuprotafib:placebo] if only 2 treatment groups). The dosage(s) for Part 1, Step 2 and Part 2 are contingent upon DRC recommendation.

Subjects will be randomized using the centralized randomization system, according to a computer-generated randomization list, and stratified by disease severity. Sentinel subject

randomization will not be stratified by disease severity. Treatment group assignment will be blinded to subjects, clinicians, Sponsor study team, Contract Research Organization (CRO) study team, and Investigators. Specific individuals from the bioanalytical CRO and Sponsor's PK group will have access to the randomization code to allow for ongoing analysis of bioanalytical samples from the subjects treated with razuprotafib and to provide PK analysis results for the DRC reviews.

2.2.3 *Study Drug*

The drug product formulation contains AKB-9778-sodium salt ready to dose, preservative free, isotonic, sterile solution (20 mg/mL or 40 mg/mL) in a 3 mL borosilicate vial fitted with a 13 mm septum and aluminum flip top seal. Placebo for razuprotafib (sterile normal saline) will be sourced locally by the site as a parenteral formulation ready to dose.

Razuprotafib will be provided in an open-label format that is compliant with International Council for Harmonisation (ICH) Good Clinical Practice (GCP) guidelines. The placebo will be sourced locally and provided with the commercially available product label.

A volume of 0.50 mL or 0.75 mL of study drug will be administered TID (Q8H) by SC injection to the abdomen. Subjects will be dosed for 7 days or until discharge from the hospital (or death), whichever occurs first. The first study drug administration must occur within 12 hours after randomization. Study drug should be administered at the same nominal times (± 1 hour) for each Q8H dose throughout the Treatment Period. Prior to the initiation of Part 2, the DRC may make a recommendation to increase the study drug dosing duration to up to 14 days.

2.2.4 *Sample Size Determination*

Part 1 will include approximately 60 subjects. In Part 1, Step 1, approximately 30 subjects (including the 6 sentinel subjects) will be enrolled. In Part 1, Step 2, approximately 30 subjects (including the 6 sentinel subjects) are planned to be enrolled. Part 2 will include approximately 120 subjects. No formal statistical assessment for sample size determination has been performed for Part 1 or Part 2. The sample size is considered adequate to provide the necessary data to evaluate the objectives for Part 1 or Part 2.

2.3 Study Endpoints

2.3.1 *Efficacy Endpoints*

The efficacy endpoints include the following:

- Proportion of subjects alive and free of respiratory failure at Day 28;
- Proportion of subjects alive and free of respiratory failure at Day 7;
- Proportion of subjects alive and not requiring invasive mechanical ventilation at any time through Day 28;
- Time to reach grade 6, 7 or 8 on the NIAID 8-point ordinal scale;
- Change in PaO₂:FiO₂ ratio from baseline to Day 7 (or discharge) and baseline to Day 28 (or discharge);

- Length of hospitalization and not requiring invasive mechanical ventilation from baseline to Day 7 and baseline to Day 28 or death;
- Length of hospitalization from baseline to Day 7 and baseline to Day 28 or death;
- Proportion of subjects who improve by ≥ 2 categories on the National Institute of Allergy and Infectious Diseases (NIAID) 8-point ordinal scale from baseline to Day 7 and baseline to Day 28;
- Proportion of subjects who worsen by ≥ 2 categories on the NIAID 8-point ordinal scale from baseline to Day 7 and baseline to Day 28;
- All-cause mortality at Day 7 and Day 28;
- Number of subjects in each category of the NIAID 8-point ordinal scale at Day 7 and Day 28;
- Time to return to prehospitalization oxygen requirement; and
- Proportion of subjects who were discharged and remained free of respiratory failure prior to Day 7 and Day 28.

The NIAID 8-point ordinal scale includes the following grades:

1. Death;
2. Hospitalized, on invasive mechanical ventilation or Extracorporeal membrane oxygenation (ECMO);
3. Hospitalized, on noninvasive ventilation or high-flow oxygen devices;
4. Hospitalized, requiring supplemental oxygen;
5. Hospitalized, not requiring supplementation oxygen – requiring ongoing medical care (COVID-19 related or otherwise);
6. Hospitalized, not requiring supplemental oxygen – no longer requires ongoing medical care;
7. Not hospitalized, limitation on activities and/or requiring home oxygen; and
8. Not hospitalized, no limitations on activities.

2.3.2 *Pharmacodynamic (PD) and Pharmacokinetic (PK) endpoints*

The PD and PK endpoints include in the following:

- Change from baseline in CRP and D-dimer;
- Change from baseline in systemic biomarkers of vascular leakage and inflammation (ie, Angpt-2, IL-6, IL-8, TNF α , and HMGB-1);
- Summary of plasma concentrations of biomarkers at each sampling time point for each treatment group; and

- Summary of plasma razuprotafib concentrations for the samples collected on Day 1 and Day 6.

2.3.3 *Safety Endpoints*

The safety endpoints include the following:

- Number of subjects with any serious adverse event (SAE); and
- Number of subjects with any treatment-emergent AE.

3 STATISTICAL METHODOLOGY

3.1 General Considerations

3.1.1 *Analysis Day*

Analysis day will be calculated from the date of first dose of study drug. The day of the first dose of study drug will be Day 1, and the day immediately before Day 1 will be Day -1. There will be no Day 0.

3.1.2 *Definition of Baseline*

Baseline is defined as the last measurement prior to the first dose of study drug.

3.1.3 *Visit Windows*

No analysis visit windows will be defined for this study, i.e., the nominal visits /time-points will be used for all statistical summaries/analyses.

3.1.4 *Summary Statistics*

Categorical data will generally be summarized with counts and percentages of subjects. The denominator used for the percentage calculation will be clearly defined. Continuous data will generally be summarized with descriptive statistics including n (number of non-missing values), mean, median, standard deviation, minimum, and maximum.

Summaries of change from baseline variables will include only patients who have both a baseline value and corresponding value at the post-baseline time point of interest.

3.1.5 *Hypothesis Testing*

All statistical comparisons will be made using two-sided tests at $\alpha = 0.05$. All null hypotheses will be of no treatment difference, and all alternative hypotheses will be two-sided. Confidence intervals will be two-sided, unless stated otherwise.

3.1.6 *Handling of Dropouts and Missing Data*

For all efficacy endpoints that do not include death as a possible outcome, data from subjects who die prior to Day 28 will be imputed at Day 28 based on the worst outcome. Other missing data for selected endpoints will be imputed using the methods as described in Section 3.4.

In cases of missing or incomplete dates (e.g. AE and concomitant medications), the missing component(s) will be assumed as the most conservative value possible. For example, AEs with missing start dates, but with stop dates either overlapping into the treatment period or missing,

will be counted as treatment-emergent, taking the worst-case approach. When partial dates are present in the data, both a partial start date and/or a partial stop date will be evaluated to determine whether it can be conclusively established that the AE started prior to the start of study drug or ended prior to the start of study drug. If the above cannot be conclusively established based on the partial and/or present dates, then the AE will be considered as treatment-emergent.

3.2 Analysis Populations

3.2.1 *Intent-to-Treat (ITT) Population*

The Intent-to-Treat (ITT) Population is defined as all subjects randomized. Subjects in this population will be analyzed according to the treatment group to which they were assigned at randomization.

3.2.2 *Full Analysis (FA) Population*

The Full Analysis (FA) Population is a subset of the ITT Population and will include subjects receive at least one dose of study drug and have at least 1 post-dose efficacy evaluation.

3.2.3 *Per-Protocol (PP) Population*

The Per-Protocol (PP) Population is a subset of the FA Population and will include subjects that have at least 1 post-dose efficacy evaluation and do not have major protocol deviations.

3.2.4 *Safety Population*

The Safety Population is defined as all randomized subjects who received at least 1 dose of study drug. Subjects in this population will be analyzed according to the study drug they actually received.

3.2.5 *Pharmacokinetic (PK) Population*

The Pharmacokinetic (PK) Population is defined as all randomized subjects who received at least one dose of study drug and had least one PK sample with plasma concentration.

3.3 Subject Data and Study Conduct

3.3.1 *Subject Disposition*

The number and percentage of subjects in each of the following categories will be presented by the treatment group and overall for all screened subjects:

- screened,
- randomized,
- treated,
- randomized but not treated,
- completed the Treatment Period, and
- completed the study.

Primary reasons for discontinuation of study treatment and primary reasons for early withdrawal from the study will be tabulated.

3.3.2 *Protocol Deviations*

Any major protocol deviation will be documented as described in the protocol deviation plan, and its impact on inclusion in each analysis population for any subject will be specified. The final list of protocol deviations impacting the analysis populations will be reviewed prior to database lock. Counts and percentages of subjects with major protocol deviations by deviation category will be summarized for all randomized subjects.

3.3.3 *Analysis Populations*

Counts and percentages of subjects in each analysis population will be summarized by treatment and in total based on all randomized subjects.

3.3.4 *Demographic and Baseline Characteristics*

The following demographic and baseline characteristics will be summarized:

- Age (years)
- Sex
- Race
- Ethnicity
- COVID-19 severity (moderate or severe)
- NIAID Assessment
- $\text{PaO}_2:\text{FiO}_2$ ratio
- Pre-hospitalization oxygen requirement (None, Low-flow or High-flow Nasal cannula or CPAP mask)
- Concomitant medication to treat COVID-19 at baseline
- Comorbid conditions (diabetes, obesity, hypertension, heart failure, chronic kidney disease)

Demographic and baseline characteristics will be summarized with descriptive statistics or counts and percentages of subjects as appropriate by treatment group and overall for each Analysis Population.

3.3.5 *Medical History*

Medical history will be coded to system organ class and preferred term using the Medical Dictionary for Regulatory Activities (MedDRA) version 23.1. Counts and percentages of subjects with medical history by system organ class and preferred term will be summarized by treatment group and overall.

Counts and percentages of subjects with COVID-19 symptoms will be summarized by treatment group and overall.

3.3.6 *Concomitant Medications*

Concomitant medications will be coded to anatomical therapeutic chemical (ATC) class and preferred term using the World Health Organization Drug Dictionary (WHO Drug Global B3, March 2020).

Prior medications will include medications which started prior to the first dose of study drug.

Concomitant medications will include medications taken on and after the first dose of study drug.

Medications that started prior to the first dose of study drug but continued into treatment are considered as both prior and concomitant.

Counts and percentages of subjects taking prior and concomitant medications by ATC class and preferred term will be summarized by treatment group and overall based on the ITT Population.

Any novel therapies for COVID-19 will be summarized based on the ITT Population.

3.3.7 *Study Drug Exposure*

Exposure to study treatment will be described in terms of duration of treatment and number of doses administered. Days of exposure to study drug will be calculated as date of last dose of study drug – date of first dose of study drug + 1. The number of doses administered for each subject will be summarized with counts and percentages in total.

3.4 Efficacy Assessment

All efficacy analysis will be performed using the ITT Population. Selected endpoints will be repeated on the FA and PP Populations. In addition, the efficacy analyses will be analyzed for pooled razuprotafib doses and placebo.

Additional analyses to understand safety and efficacy variables further may be carried out and will be labeled as post-hoc analyses.

3.4.1 *Efficacy Endpoints*

The following parameters will be analyzed using Cochran-Mantel-Haenszel (CMH) test stratified by disease severity:

- Proportion of subjects alive and free of respiratory failure at Day 28;
- Proportion of subjects alive and free of respiratory failure at Day 7;

All results will be summarized descriptively by treatment arm and expressed as proportions, along with corresponding 95% CI of the difference between response rates, and p-values. The 95% CI will be constructed using the normal approximation method.

Additional Analysis may be considered by incorporating other covariate adjustments into the analysis.

Respiratory failure will be defined as subjects who are on invasive mechanical ventilation; are receiving oxygen delivered by high-flow nasal cannula (heated, humidified, oxygen delivered via reinforced nasal cannula at flow rates >20 L/min with fraction of delivered oxygen ≥ 0.5) noninvasive positive pressure ventilation or extracorporeal membrane oxygenation; or have a

clinical diagnosis of respiratory failure (ie, clinical need for 1 of the preceding therapies, but preceding therapies not able to be administered in setting of resource limitation). Subject who die prior to the study timepoint (Day 7 or Day 28) will be imputed based on the worst outcome. Other missing responses will be imputed using a multiple imputation (MI) method under the assumption of missing at random (MAR).

Sensitivity Analysis

- All missing responses will be considered as non-responders and which will be imputed taking the worst case approach.
- The analysis will be repeated on FA and PP Populations.

The following parameters will be analyzed using the CMH test as stated above:

- Proportion of subjects alive and not requiring invasive mechanical ventilation at any time through Day 28;
- Proportion of subjects who improve by ≥ 2 categories on the NIAID 8-point ordinal scale from baseline to Day 7 and baseline to Day 28;
- Proportion of subjects who worsen by ≥ 2 categories on the NIAID 8-point ordinal scale from baseline to Day 7 and baseline to Day 28;
- All-cause mortality at Day 7 and Day 28; and
- Proportion of subjects who were discharged and remained free of respiratory failure prior to Day 7 and Day 28.

The following parameters will be analyzed using an analysis of variance (ANOVA) model with effects for treatment, baseline value and disease severity as factors:

- Change in $\text{PaO}_2:\text{FiO}_2$ ratio from baseline to Day 7 (or discharge) and baseline to Day 28 (or discharge),
- Length of hospitalization and not requiring invasive mechanical ventilation from baseline to Day 7 and baseline to Day 28 or death,
- Length of hospitalization from baseline to Day 7 and baseline to Day 28 or death,

Missing responses will be imputed using a multiple imputation (MI) method under the assumption of missing at random (MAR).

All results will be summarized descriptively by treatment group, along with corresponding 95% CI of the difference between razuprotafib groups vs. placebo, and p-value.

The length of hospitalization will include all days that the subject is admitted to the hospital. For subjects who are discharged and readmitted to the hospital, the length of hospitalization will include the days after readmission.

Hospitalization days will be counted in 24-hour periods; any partial days will be counted as a whole day.

Days that subjects are on the ventilator will be counted as days of respiratory failure. Days that subjects are of respiratory failure based on the definition will be counted as days of respiratory failure. For subjects receiving high flow oxygen by a nasal cannula or noninvasive positive

pressure ventilation when enrolled, the length of respiratory failure will include all the days of respiratory failure from baseline.

The time-to-event endpoint of time to reach grade 6, 7 or 8 on the NIAID 8-point ordinal scale will be summarized descriptively using the Kaplan-Meier method. The Kaplan-Meier estimate of the median time as well as the 2-sided 95% confidence interval will be presented by treatment group.

The endpoint of number of subjects in each category of the NIAID 8-point ordinal scale at Day 7 and Day 28 will be summarized by treatment group and timepoint using descriptive statistics.

The endpoint of time to return to prehospitalization oxygen requirement will be summarized by treatment group using descriptive statistics.

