9.2.1 Analysis of Efficacy

Continuous efficacy endpoints will be analyzed using an analysis of variance model with effects for treatment and disease severity as factors.

Binary efficacy endpoints will be analyzed using a Cochran-Mantel-Haenszel test stratified by disease severity.

For all efficacy endpoints that do not include death as a possible outcome, data from subjects who die prior to Day 28 will be imputed at Day 28 based on the worst outcome.

All efficacy analyses will be performed using the ITT Population. The efficacy analyses will be repeated on the PP Population.

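### SAP 3.4.1 pairs a severity-stratified CMH test with a 95% CI for which no strata, weights or variance are stated

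*SAP*

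**What the plan says.** On the test, the two documents agree. Protocol 9.2.1: "Binary efficacy endpoints will be analyzed using a Cochran-Mantel-Haenszel test stratified by disease severity". SAP 3.4.1, for freedom from respiratory failure while alive at Day 28 and Day 7: "The following parameters will be analyzed using Cochran-Mantel-Haenszel (CMH) test stratified by disease severity". SAP 3.4.1 then applies the CMH approach to the remaining binary endpoints.

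Severity is also the randomisation stratum. SAP 2.2.2 describes a "computer-generated randomization list, and stratified by disease severity", except for the 6 sentinel subjects in each step of Part 1.

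On the interval, SAP 3.4.1 asks for proportions by arm, "along with corresponding 95% CI of the difference between response rates, and p-values. The 95% CI will be constructed using the normal approximation method". It does not say whether the difference is crude or stratum-weighted, and it gives no weights or variance formula. The Protocol gives no interval method. The only reference to adjustment is optional and concerns further covariates: "Additional Analysis may be considered by incorporating other covariate adjustments into the analysis".

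Missing responses other than deaths are multiply imputed under missing at random (SAP 3.4.1). Part 2 has about 120 subjects, allocated 1:1:1 or 2:1 (SAP 2.2.4 and 2.2.2), with moderate disease capped at about half (Protocol 3.1).

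**The concern.** The p-value comes from a comparison within severity strata. The interval, read literally, ignores them. Estimate and test would then rest on different variances, and a report could show p<0.05 beside an interval that includes 0.

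Severity should matter a good deal here. The severe criteria in Protocol 4.1 admit patients on high-flow nasal oxygen or noninvasive positive pressure ventilation. The definition in SAP 3.4.1 counts noninvasive ventilation, and high-flow oxygen above stated thresholds, as respiratory failure. Some severe subjects can therefore enter already failing the first-listed endpoint. A crude variance includes that between-stratum variation, which stratified randomisation has largely balanced out.

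The SAP has no formal sample-size basis (2.2.4), so readers will lean on the interval to judge what the trial has and has not ruled out. The continuous endpoints in SAP 3.4.1 already carry a severity term, so the binary intervals are the exception.

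**Working it through.** There is no power, event-rate or precision figure in the plan to reproduce. All response rates and effects below are assumptions, written as moderate/severe.

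**1. Width under no effect.** With equal arms and proportional weights:

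SE ratio = sqrt(mean within-stratum p(1-p) / overall p(1-p)).

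For 95/60 and a 50/50 split:
- within strata: (0.95×0.05 + 0.60×0.40)/2 = (0.0475 + 0.24)/2 = 0.1438
- overall: p = 0.775, p(1-p) = 0.1744
- SE ratio = sqrt(0.1438/0.1744) = 0.908. The crude interval is 1/0.908 = 1.10 times as wide.
- equivalent sample size: 0.1744/0.1438 = 1.21, or 21% more subjects.

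The same formula gives 0.16/0.15 = 1.07 (7%) for 90/70 and 0.1994/0.1488 = 1.34 (34%) for 95/50. With 25% moderate the three figures fall to 12% (95/60), 4% (90/70) and 19% (95/50).

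Simulation at 40 v 40 under 95/60, 50/50 and no effect gives a crude half-width of 18.1 points with about 97% coverage. A Mantel-Haenszel (MH) stratified Wald interval gives 16.2 points with 93.9%.

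**2. A table where test and interval disagree.** Take 40 v 40 with 20 per stratum per arm. Active: 20/20 moderate, 11/20 severe. Placebo: 16/20 and 7/20.
- CMH: observed minus expected is 20-18 = 2 and 11-9 = 2. The null variances are 0.923 and 2.538. Chi-square = 4²/3.462 = 4.62, p = 0.032.
- Crude: 31/40 - 23/40 = 0.200. SE = sqrt(0.775×0.225/40 + 0.575×0.425/40) = 0.1023. CI -0.0005 to 0.4005.
- MH-stratified Wald: both stratum differences are 0.20, with weights of one half. SE = sqrt(0.25×(0.0080 + 0.02375)) = 0.0891. CI 0.025 to 0.375.

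**3. How often they disagree.** The table gives the share of simulated trials, at a 50/50 split, in which CMH p<0.05 and the CI excluding 0 do not coincide. CMH is without continuity correction.

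| Size | Assumed rates | Assumed gain | Crude Wald | MH-stratified Wald |
|---|---|---|---|---|
| 40 v 40 | 95/60 | none | about 2% | about 1% |
| 40 v 40 | 95/60 | 3/25 points | 4.1% | 4.0% |
| 40 v 40 | 90/70 | 5/15 points | 1.0% | 2.8% |
| 40 v 40 | four pairs* | none | 0.3-2.1% | 1.1-1.2% |
| 40 v 40 | four pairs* | 15 points each** | 0.3-6.4% | 2.5-3.2% |
| 80 v 40 | 95/60 | 3/25 points | 12% | 5.1% |
| 80 v 40 | four pairs* | none | 1.2-1.8% | 1.1-1.8% |
| 80 v 40 | four pairs* | 15 points each** | 5.8-10.3% | 2.2-6.4% |

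*75/75, 85/65, 95/55 and 80/40. **Moderate rate capped at 99%.

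Where strata differ strongly, nearly all the crude disagreements are p<0.05 with an interval that includes 0. The 80 v 40 layout arises in Part 2 under 2:1 allocation or, with two doses, in the pooled-dose comparison that SAP 3.4 calls for. Single-dose comparisons under 1:1:1 are 40 v 40.

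**The case against.** **The SAP never says crude.** A reader might infer that an unstratified interval has been specified. The text does not go that far. The interval sentence follows the stratified test and calls the interval the corresponding one. An MH-weighted difference with a Wald interval is also a normal approximation, and SAP 7 leaves programming detail to a separate document. This stands: what can be shown is that the estimator, weights and variance are unstated, with the crude interval as the literal reading.

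**Disagreement is not caused only by missing strata.** CMH uses a null variance, so any separately built interval will sometimes conflict with it. This also stands. At 40 v 40 a stratified Wald interval did no better under 95/60 with gains of 3/25 points, and did worse at 90/70. One stratified Newcombe version disagreed in 7.7% of trials at 40 v 40 with the 3/25 gains, against 4.2% for crude in the same run. At 80 v 40 stratified Newcombe disagreed in about 2-3%.

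**The error is in the safe direction.** A reader might infer false precision or extra false positives. Where strata differ strongly the crude interval over-covers. Where they are alike it nearly coincides with the stratified one: 1.3% wider at 40 v 40 with equal rates.

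**Score-type intervals complicate pooling.** An estimate with an SE combines across imputations directly. Newcombe and Miettinen-Nurminen limits need an extra rule. Newcombe versions also differ: at 40 v 40 with no effect, half-widths ran from 16.2 to 18.2 points. This stands and shapes the fix.

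None of it supplies the missing specification.

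**Conclusion.** The point holds as a gap in specification with a modest cost. The test is stratified by the randomisation factor. The interval has no stated strata, weights or variance and reads as crude. If programmed that way, and if severity is strongly prognostic, it would be conservative: about 10% wider under 95/60, a 50/50 split and no effect, equivalent to about 21% more subjects. The range is 7% to 34% over 90/70 to 95/50, and less if fewer than half are moderate.

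It could also include 0 when CMH p<0.05. The 12% figure is the high end, from 80 v 40 with a large gain confined mostly to severe subjects. It should not be read as typical. Nor would stratifying the interval make it always agree with CMH.

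The sizes rest on assumed rates and effects, because the documents give none. The unstratified sentinel subjects (6 per Part 1 step) do not affect Part 2. The change is worth making because it is cheap and brings the reported estimate and the test onto the same stratification.

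**What to change.** In SAP 3.4.1, for every endpoint tested by CMH, report the MH-weighted risk difference across severity strata with a stratified 95% CI. State:
- the weights, for example n1·n0/(n1+n0) within each stratum;
- the variance or interval method, naming the exact version;
- how the estimate and interval are combined across multiple imputations.

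A stratified score-type interval (Miettinen-Nurminen or Newcombe) is preferable where it can be pooled, because stratified Wald covers slightly below 95% at these sizes (about 93.5-94%). If a stratified Wald interval is kept for ease of pooling, the SAP should say so and acknowledge the slight under-coverage.

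The cost is a few sentences of SAP text and some programming, with no new data. The downside is having to choose an interval version and, for score-type limits, adding a pooling step.
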